Appendix 10 Eastern Cooperative Oncology Group Performance Status

Grade	Description
0	Fully active, able to carry on all pre-disease performance without restriction
1	Restricted in physically strenuous activity but ambulatory and able to carry out work of a light or sedentary nature, for example, light housework, office work
2	Ambulatory and capable of all self-care, but unable to carry out any work activities; up and about > 50% of waking hours
3	Capable of only limited self-care, confined to bed or chair > 50% of waking hours
4	Completely disabled; cannot carry on any self-care; totally confined to bed or chair
5	Dead

CCI

Appendix 12 Model for Bayesian Dose Escalation

The Bayesian model results are based on the number of DLTs and evaluable participants per dose level (DL). The SMC will receive results of a Bayesian two-parameter logistic regression model updated with the observed DLT data (Neuenschwander 2008), including a recommendation for the next dose. For a DL d_j , the relationship between dose and probability of toxicity P (DLT) is defined by:

$$P(DLT|d_j, \alpha, \beta) = \frac{\exp\left(\alpha + \exp(\beta) * \log\left(\frac{d_j}{d_{ref}}\right)\right)}{1 + \exp\left(\alpha + \exp(\beta) * \log\left(\frac{d_j}{d_{ref}}\right)\right)},$$

with bivariate normally distributed parameters (α, β) using the following parameterization:

- Pre-selected DL $d_j \in \{50 \text{ mg}, 100 \text{ mg}, 200 \text{ mg}, 400 \text{ mg}, 600 \text{ mg}\}$
- Reference dose $d_{ref} = 800 \text{ mg}$

C [REDACTED]
C [REDACTED]
L [REDACTED] [REDACTED] [REDACTED]

The following toxicity regions (Table 22) will be defined:

Table 22 Toxicity Intervals

Toxicity intervals	Probability of DLT	Loss term (weight in loss function)
Under-Dosing	[0.0, 0.20)	1
Target toxicity	[0.20, 0.35]	0
Excessive toxicity	(0.35, 0.60]	1
Unacceptable toxicity	(0.60, 1.00]	1.5

DLT = dose limiting toxicity.

The model-based recommendation for the next DL is the DL that minimizes the loss function. The loss function is defined as the sum of products of the probability to lie within each of the toxicity regions, and the associated loss term:

- $1 \times P(\text{Under-Dosing}) + 0 \times P(\text{targeted toxicity}) + 1 \times P(\text{excessive toxicity}) + 1.5 \times P(\text{unacceptable toxicity})$.
- Increase of DLs is limited by 100% of the highest current total daily DL.

The model will be provided with the following pre-selected DLs: 50 mg, 100 mg, 200 mg, 400 mg, 600 mg. The set of doses can be changed any time by the SMC.

The target DLT probability for the MTD is 30%.

The SMC will be notified of a potential MTD once the estimate for DLT probability of a potential MTD reaches sufficient precision, i.e.:

- The upper bound of the one-sided 95% credible interval is not more than 40%,
- and the estimated DLT probability for the suggested MTD is in [17%-30%].

In case information arises from other studies that changes current knowledge on the dose toxicity relationship, the prior distribution will be updated prior to the first participant being treated in this study. This change will be documented in the SMC charter. If changes are needed due to a change in regimen, these will also be documented in the SMC charter prior to first SMC with participants with new regimen.

The Bayesian model used in Part 1A will be used continuously to also monitor the toxicity results in Part 1B with all participants. Unacceptable toxicity in the food effect cohort is defined as AEs that meet the DLT criteria (as defined in Section 6.6) regardless of when they occur during treatment.

Posterior distribution and the recommended next DL suggested by the model will be calculated using SAS Version 9.4 or higher, EAST Version 6.5 or higher, or R Version 3.5.1 or higher with library package bcrm ([Sweeting 2013](#)) or package CRMPack ([Bové 2019](#)).

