6.6.2 Dose-limiting Toxicities – Definition and Criteria

A DLT is defined as any of the following AEs according to the National Cancer Institute Common Terminology Criteria for Adverse Events (NCI-CTCAE) Version 5.0 assessed by the Investigator and/or the Sponsor at any dose, judged not to be related to the underlying disease or any previous or concomitant medication or concurrent condition, occurring during the DLT observation period, which for Part 1A starts on the first day of study intervention (Day 1) and has a duration of 21 days.

Study accrual will be halted, pending discussions with the SMC or the study Sponsor, if there is an occurrence of a Grade 5 toxicity by the NCI-CTCAE Version 5.0 attributable to the treatment regimen or if more than 1 DLT is seen in DL 1 in Part 1A.

The treatment of toxicities with transfusions or growth factors (e.g., granulocyte-colony stimulating factor, erythropoietin) is not permitted during the DLT period and if it occurs will be considered a DLT.

AEs judged as DLT will include:

- Any Grade ≥ 3 non-hematologic AE with exception of:
 - Single laboratory values out of normal range that have no clinical correlate and resolve to Grade ≤ 1 or to baseline within 7 days with adequate medical management or asymptomatic Grade 3 lipase or amylase elevation (> 5 ULN) not associated with clinical manifestation of pancreatitis.
 - Infusion-related reaction resolving within 6 hours from the end of infusion and controlled with medical management (for iv compounds only)
 - Diarrhea persisting < 72 hours after initiation of medical management
 - Nausea and vomiting of ≤ 72 h duration with adequate and optimal therapy
 - Transient (≤ 72 h) fatigue, local reactions, flu-like symptoms, fever, headache, hypertension that resolves to Grade ≤ 1 with adequate treatment
 - Grade 3 non-recurrent skin toxicity that resolves to Grade ≤ 1 in less than 7 days after initiation of medical management
 - Tumor flare phenomenon defined as local pain, irritation, or rash localized at sites of known or suspected tumor that resolve to Grade ≤ 2 within 6 days
 - Any death clearly due to the underlying disease or extraneous causes

- Grade ≥ 3 neutropenia with clinical signs/symptoms, such as fever $> 38.5^{\circ}\text{C}$ (e.g., for febrile neutropenia, an ANC $< 1000/\text{mm}^3$ with single temp of 38.3°C [101°F] or a sustained temperature of $\geq 38^{\circ}\text{C}$ [100.4°F] for more than one hour)

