9.4.2.1 Part 1A: Dose Escalation

Analyses to decide on dose escalation will be performed on the DLT set and will be based on available safety and preliminary PK data. To support the decision on dose escalation, the SMC will receive results of a Bayesian dose-toxicity model, including the recommendation of next DL. This Bayesian dose-toxicity model ([Neuenschwander 2008](#)) is further specified in [Appendix 12](#). For each SMC meeting, the model will be updated with the number of DLTs and evaluable participants per DL.

Potential DLs are: 100 mg (starting dose), 200 mg, 400 mg, 600 mg. However, the SMC may decide to have different, or additional DLs or skip DLs (total daily dose increases must not exceed 100% of the highest total daily DL currently considered safe). Based on the observed toxicity profile and available PK and Pd, DL(s) that are different to, or higher or lower than the prespecified DLs may be tested.

The dose suggested by the model for the next cohort will be based on [minimizing the Bayesian Risk](#).

The SMC may choose a different dose than suggested by the Bayesian escalation approach. Also, the SMC may decide to change the dosing regimen. In such a case the dose-toxicity model will be extended, or a separate model will be set up using the information from previous cohorts to define a new prior information for the new schedule.

The MTD will be defined by the SMC. The target DLT probability for the MTD is 30%.

Usually, decisions on dose escalation are taken once all participants of the most recent cohort have completed the DLT period or dropped out. In exceptional cases, however, the SMC may decide on the next cohort earlier, i.e., before the last participant of a cohort has finished the DLT

period (considering the model recommendation). Per definition of the DLT analysis set, participants who have not completed the DLT period are not included for update of the model, unless they experienced a DLT. However, data of such participants will be included at next SMC.

Details on analyses for SMC will be described in the SMC iAP.

[figure not shown]
Before first dosing, the assumed relationship between DL and toxicity is specified through the prior distribution. The prior distribution chosen for this study corresponds to the following (Table 18):

CCI

██████████	████	████	████	████	████
████	████	████	████	████	████
████	████	████	████	████	████

DLT = Dose limiting toxicity.

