9.4.4 Sequence of Analyses

SMC for Part 1A: The SMC will review available data during study conduct. The cut-off for dose escalation assessments by the SMC will usually be triggered by the completion of the DLT period (or dropout) of the last participant in the respective dose escalation cohort of usually 3 participants. When enrolment of last participant in a dosing cohort is delayed, the SMC may decide (based on available data) upon enrolment and dose for the next dosing cohort before all participants in a cohort have completed 21 days. The Bayesian model will then be updated with the available data, and the data from the participant not having completed the DLT period at time of SMC will be considered in the next SMC. In these cases, cut-off can be earlier (after DLT period of the first 2 subjects is finished or they experienced a DLT).

SMC for Part 1B: The cut-off of the SMC will be triggered when the 6th participant has been treated for 28 days (or has dropped out). The SMC will be supported by the results of the Bayesian model used in Part 1A.

Primary analysis for dose escalation

The cut-off for an exploratory analysis of the safety, available PK, available Pd and preliminary antitumor activity data from Part 1A will be triggered when all participants have reached either the first on-treatment tumor assessment, or experienced death or premature withdrawal for any reason, whichever comes first.

Final Analysis for Part 1A and 1B

Follow-up analyses to report further efficacy, safety, and PK data if applicable for Part 1A and all analyses for Part 1B will be performed once the End of Study has been reached.

Additional Analyses

Further analyses may be performed, e.g. for publication purposes or decision-making purposes.

More details will be described in the iAP.

10

References

Curtin NJ. DNA repair dysregulation from cancer driver to therapeutic target. *Nat Rev Cancer*. 2012;12:801-17.

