- SAE reporting on a paper report form is used as a back-up method for an EDC system failure. The form includes completion instructions for the Investigator, names, addresses,

and telephone and fax numbers. All information from the paper form will be transcribed into the electronic form as soon as the system becomes available.

- Facsimile transmission (fax to mail) of the paper form or any follow-up information is the preferred method for transmission and will be done within 24 hours to the Sponsor or its designee.
- In rare circumstances and in the absence of facsimile equipment, notification by telephone is acceptable with a copy of the form sent by overnight mail or courier service.
- Initial notification via telephone does not replace the need for the Investigator to complete and sign the form within 24 hours after becoming aware of the event.
- Additional documents (e.g. laboratory reports, autopsy report, hospital discharge letter) and relevant pages from the CRF may be required in addition (e.g. medical history, concomitant medication). The data provided will be consistent with the information in the CRF.

Recording and Reporting of DLTs

- Each event that meets the DLT criteria, as specified in Section 6.6.2, will be recorded in the CRF within 24 hours after awareness of the event.
- Serious DLTs will be reported in an expedited manner, using the SAE reporting process, as specified above.
- Notification of each DLT related event (non-serious and serious) will be reported to the Sponsor or its designee within 24 hours from the date of awareness.

Reporting of AESIs

- For a non-serious AESI, the site will complete the specific AESI report form and notify the Sponsor immediately (within 24 hours), using the same process for reporting SAEs, as specified above.
- For a serious AESI, the site will complete an SAE report form, using the SAE reporting process, specified above.

Reporting of Pregnancies

- Pregnancy will be reported whether related to the study intervention using the applicable paper form.
- The applicable form will be used to report if an abnormal outcome of the pregnancy occurs and the child/fetus sustains an event.
- Facsimile transmission (fax to mail) of the paper form or any follow-up information is the preferred method for transmission and will be done within 24 hours to the Sponsor or its designee.

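### The prior or model for a new dosing regimen may be documented after that regimen's first DLT results can be known

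*Protocol*

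**What the plan says.** Protocol Appendix 12 sets two deadlines next to each other:

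- If other studies change what is known about dose and toxicity, "the prior distribution will be updated prior to the first participant being treated in this study".
- If the regimen changes, the model changes follow a later clock: "these will also be documented in the SMC charter prior to first SMC with participants with new regimen".

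Protocol Section 9.4.2.1 covers what happens to the model. Either the existing one is extended, or "a separate model will be set up using the information from previous cohorts to define a new prior information for the new schedule". It dates neither option.

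The surrounding text fixes the timing and who knows what:

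- Section 9.4.4: the SMC cut-off "will usually be triggered by the completion of the DLT period (or dropout) of the last participant in the respective dose escalation cohort".
- Section 6.6.2: the DLT window "starts on the first day of study intervention (Day 1) and has a duration of 21 days".
- Section 6.3.2: the study is open-label.
- Appendix 4 (recording and reporting of DLTs): notification of each event "will be reported to the Sponsor or its designee within 24 hours from the date of awareness".
- Appendix 2 (study governance): the SMC is made up of investigators and Sponsor representatives, including the biostatistician.

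A regimen change is a foreseen option. Sections 4.1.1 and 6.6.1 allow it, and Appendix 7 sets out five alternative schedules.

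**The concern.** A posterior means what it claims only if the prior was settled without regard to the data that then enter through the likelihood. Here the stated deadline is the meeting at which the new cohort's DLT counts are fed into the model. Someone choosing among several defensible priors, or several ways of extending the model, could by then know the result.

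With cohorts of about 3, the prior carries much of the weight. At stake are the model's dose recommendation, the notification of a potential MTD, and the DLT probabilities that summarize the primary objective.

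**Working it through.** **1. Timeline.** Let T be the first dosing day of the last participant in the first new-regimen cohort.

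- The DLT window runs 21 days from T, and the SMC cut-off usually waits for it to end or for that participant to drop out.
- The latest compliant documentation date is therefore normally at least 21 days after T.
- Section 9.4.4 allows an earlier cut-off, but only once the first two participants have finished the window or had a DLT. Even then, most of a three-person cohort is known.
- The other deadline in Appendix 12 falls before anyone is dosed.

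**2. Does other text close the gap?** Section 9.4.2.1 points to previous cohorts as the source for a separate model's prior. That limits the intended source but gives no date, and it sets no such limit for an extended model. Section 6.6.2 has the SMC confirm DLTs, but the Sponsor has the reports before that. Nothing in the available documents requires the new-regimen prior to be fixed before first dosing.

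**3. Does it reach the reported analysis?** Yes. SAP Section 15.1 takes the logistic model from the SMC analysis plan or, where the model was changed, from the SMC charter. The same section derives the model-based MTD suggestion.

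**4. Size (illustration only).** The plan states no figure to reproduce and the prior is redacted. I used the Appendix 12 model, logit P(DLT at dose d) = α + exp(β)·log(d/800), with independent normal priors. The Table 22 loss is P(rate < 0.20) + P(0.35 < rate ≤ 0.60) + 1.5·P(rate > 0.60), minimized over 50, 100, 200, 400 and 600 mg. The 100% cap on dose increases was not applied. Where earlier cohorts are included, they are assumed to be 0/3 at 100 mg and 0/3 at 200 mg and enter at full weight.

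*4a. Choice among fixed priors.* Median DLT rate at 800 mg of 25%, 40% or 55%; SD(α) 1.5; β ~ N(0, 0.7²). Prior mean DLT rate at 400 mg: 20%, 29%, 39%. Minimum-loss dose (mg) under the three priors:

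| Cohort at 400 mg | No earlier data | With earlier cohorts |
|---|---|---|
| 1/3 DLTs | 400, 400, near-tie of 400 and 200 | 600, 400, 400 |
| 2/3 DLTs | 200, 100, 100 | 400, 400, 400 |

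In the near-tie the losses are 0.7807 at 400 mg and 0.7808 at 200 mg, so a coarse grid can tip it either way. With 1/3 and no earlier data, P(rate > 35%) at 400 mg is 26%, 36% and 46%. This part shows sensitivity to the prior. Nothing is counted twice in it.

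*4b. Same cohort counted once, then twice.* This is the extreme form of a prior informed by the cohort. Assumed priors: median rate at 800 mg of 30% or 50%, each with SD(α) 1.5 and SD(β) 0.75, or SD(α) 2 and SD(β) 1; mean β 0. Earlier cohorts as above, then 2/3 at 400 mg:

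| Prior (median; SDs) | Mean at 400 mg, once → twice | Minimum-loss dose |
|---|---|---|
| 30%; 1.5, 0.75 | 29.7% → 39.6% | 400 → 200 mg |
| 30%; 2, 1 | 32.6% → 43.2% | 400 → 200 mg |
| 50%; 1.5, 0.75 | 34.6% → 43.4% | 400 → 200 mg |
| 50%; 2, 1 | 36.4% → 46.1% | 400 → 200 mg |

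The effect depends on the outcome. With 0/3 at 400 mg the minimum-loss dose stays at 600 mg under all four priors. With 1/3 it changes under one of the four (600 to 400 mg).

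**The case against.** The strongest reply has four parts.

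- **Nothing prescribes double use.** The Appendix 12 sentence governs when changes are documented, not when they are chosen or from what data, and Section 9.4.2.1 names previous cohorts as the source. This stands. A reader might infer that the plan uses the new cohort's data twice; the documents do not support that. They only fail to rule it out. The documentation date still matters, because an earlier but unrecorded choice cannot be verified.
- **Other documents may set an earlier date.** The SMC charter and the SMC analysis plan are not available here. Either could do so, but the protocol would still permit the later one.
- **The model is advisory.** A regimen change is optional, the SMC may depart from the recommendation and itself defines the MTD, and a frequentist analysis without a prior is planned (protocol Table 17, SAP Section 15.1). This limits the practical consequence. It does not repair the reported posterior.
- **The numbers are soft.** A reader might take from 4a that one DLT in 3 shifts the recommendation by a full dose step depending on the prior. Without earlier data that rests on a near-tie. With earlier cohorts, as Section 9.4.2.1 implies, the 2/3 contrast disappears, although some sensitivity remains at 1/3 (600, 400, 400 mg). No general claim of a full dose step is justified.

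**Conclusion.** The point holds as a gap in the wording. The deadline for a new-regimen prior or model extension normally falls after the DLT results it will be combined with can be known, and the plan contains no dated safeguard. The same data could therefore influence both prior and likelihood, and a charter-documented change would carry into the final Bayesian analysis.

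The size is unknown. The 4b result, a rise of about 9 to 11 percentage points in the mean DLT probability at 400 mg (for example 43.4 − 34.6 = 8.8 and 43.2 − 32.6 = 10.6) with a change in minimum-loss dose, rests on assumed priors, assumed earlier cohorts and full double counting. It shows that real reuse of the data could matter with cohorts of 3; it does not predict what happens in this trial. The point arises only if the regimen is changed.

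**What to change.** In Appendix 12 and the SMC charter, replace the deadline for regimen-driven changes with this rule: the new-regimen prior or model extension is documented and dated before the first participant is treated on the new regimen, and uses only data available up to that date. State that this covers both routes in Section 9.4.2.1, the extended model and the separate model. This brings regimen changes into line with the before-treatment standard that Appendix 12 already applies to information from other studies.

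The cost is one sentence in each document and no extra participants. The drawback is timing: the charter update must be finished before the regimen starts, rather than during the cohort's DLT period.

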Appendix 13 Protocol Amendment History

The information for the current amendment is on the title page.

Protocol Version 3.0 (25-Oct-2021)

The overall rationale for this amendment is based on the need to update the adverse events of special interest (AESI) information in this protocol.

Section # and Name	Description of Change	Brief Rationale
Title page	Title page modifications in placement of version reporting and removal of other information.	To follow internal quality standards for clinical study protocols.
1.3.1 Table 1 Schedule of Activities: M4076 Monotherapy Dose Escalation (Daily Dosing), Part 1A.	For DLT Period Day 1, a window period of '- 1 day' was added to specific assessments. Additional text was added to the Medical history regarding the collection of information pertaining to tobacco use. Added requirement for extended follow-up of SAEs and AESIs.	A Visit window was added for participant flexibility. To provide transparency and clarity that this information is being collected for potential use in PK assessment. For consistency with Section 8.3.6.
1.3.2 Table 2: Schedule of Activities: Preliminary Food Effect Assessment, Part 1B.	Prohibition of tissue samples of bone biopsies for CCI submission.	Limited tumor cellularity in biopsies obtained from bone(s) is insufficient to perform C analysis. CI
1.3.3 Table 4 Part 1B Preliminary Food Effect Assessment: PK, ECG and CCI Assessments	Urine collection interval for PK was further specified.	Clarification.
2.1 Study Rationale 2.2 Background 2.3.2 Benefit Assessment	Removed mention of ataxiatelangiectasia and rad3-related (ATRi) combination.	No longer needed in this protocol.
2.3 Benefit/Risk Assessment	Added required text per Merck protocol standards.	To follow internal quality standards for clinical study protocols.
5 Study Population Appendix 2 Study Governance (Informed Consent Process)	Textual changes regarding legal or legally authorized representative.	To follow internal quality standards for clinical study protocols.
5.3 Lifestyle Considerations	Added that tobacco use status (former, current, never) will be collected at screening and recorded in the eCRF.	To evaluate potential impact of tobacco use on PK, efficacy, and safety.

Section # and Name	Description of Change	Brief Rationale
6.6.2.1 Table 10 M4076 Recommended Dose Modifications	'Grade 3 Hematologic and Nonhematologic ADRs' was added in the Table title and 'hematologic' was added in the Table header.	To include hematologic toxicities for clarity and consistency with the requirements already stated in this section.
Section 8.3 Adverse Events and Serious Adverse Events (AE/SAE detection method)	Added sentence referencing to Appendix 4 for information regarding recording, evaluating, and assessing causality of AEs and SAEs and procedures for completing and transmitting SAE reports.	To follow internal quality standards for clinical study protocols.
8.3.6 Adverse Events of Special Interest CCI	Added definition of AESIs of cytopenia.	To allow closer monitoring of AEs consistent with the potential risk of cytopenia.
9.4.3 Other Analyses Table 19 Part 1 Other Analyses	Concentration-QTc analysis details are specified.	Clarification.
Appendix 4 Adverse Events: Definitions and Procedures for Recording, Evaluating, Follow-up, and reporting (adverse event/serious adverse event detection method)	Update of text regarding guidance to the Principal Investigator.	To follow internal quality standards for clinical study protocols and clarifications to the text for better understanding of guidance of adverse events/serious adverse events definition.
Throughout	Removal of Overall Survival and mention of Survival Follow-up.	To align with standard Phase 1 study design template, where no overall survival is included.
Throughout	Minor editorial and document formatting revisions.	Minor; therefore, have not been summarized.

ADR = adverse drug reaction; AE = adverse event; AESI = adverse event of special interest; ATR = ataxia telangiectasia; DLT = dose limiting toxicity; ECG = electrocardiogram; eCRF = electronic case report form; PD = pharmacodynamic; PK = pharmacokinetic; QTc = Corrected QT Interval; SAE = serious adverse event.

Protocol Version 2.0 (07-Apr-2021)

Overall Rationale for the Amendment

The overall rationale for this amendment is based on the fact that the full toxicity profile of M4076 remains unknown in humans; therefore, measures regarding concomitant medications and dose modifications were adopted.

Section # and Name	Description of Change	Brief Rationale
1.3.1 Part 1A – M4076 Monotherapy Dose Escalation (Daily Dosing)	Added the Part 1A fasting window information	For clarity
1.3.2 Part 1B	Added the Part 1B fasting window information	For clarity
Table 1: Part 1A Schedule of Activities	Fasting window added to the "Study Intervention Administration" row.	For clarity
Table 2: Part 1B Schedule of Activities	Fasting window added in the "Low-fat Meal or Overnight Fasting" row. Vital signs assessments timing note added.	For clarity
Table 3: Part 1A M4076 Monotherapy Dose Escalation: Pharmacokinetic, ECG and Pharmacodynamics Biomarker Assessments	Added a footnote outlining fasting window.	For clarity
Table 4: Part 1B Preliminary Food Effect Assessment: Pharmacokinetic, ECG and Pharmacodynamics Biomarker Assessments	Added a footnote outlining ECG fasting window.	For clarity
4.1.1 Part 1A – M4076 Monotherapy Dose Escalation	Added reference to fasting window information in Section 6.1. Added note that, in determining the RDE, the SMC will additionally consider PK and Pd information. Removed the following sentence: If MTD is not reached, the SMC may define the RDE based on the PK, Pd, and safety profile.	For completeness and clarity
4.1.2 Part 1B- Preliminary Food Effect Assessment	Added reference to fasting window information in Section 6.1.	For clarity.
5.1 Inclusion Criteria	Updated Inclusion Criterion of CLcr from 30 mL/min to 60 mL/min by Cockcroft-Gault equation	Safety measure in this FIH study.
5.2 Exclusion Criteria	Added the following bullets: 
 • A history of additional risk factors for Torsades de Pointes (e.g., clinically relevant hypokalemia, family history of Long QT Syndrome) 	As additional safety measures.

Section # and Name	Description of Change	Brief Rationale
	
 The use of concomitant medications that prolong the QT/QTc interval 	
5.2 Exclusion Criteria; 6.5.2 Permitted Medicines; 6.5.3 Prohibited Medicines	As appropriate in respective sections, added information regarding exclusion of irinotecan, oral direct thrombin inhibitors, digoxin, and proton pump inhibitors with time window caveats for acceptable administration of H2-receptor antagonists and antacids	For clarity and to avoid potential effect of concomitant administration.
6.1 Study Intervention Administration	Added Parts 1A and 1B fasting window information	For clarity
6.6.2 Dose-limiting Toxicities – Definition and Criteria	Added that the possibility of Hy's Law parameters as listed will require prompt permanent discontinuation from the study.	As additional safety measure
6.6.2.1 Dose Interruptions and Modifications; Table 10	
Modified as follows as it pertains to text and Table 10:
 
 To require permanent discontinuation of M4076 for Grade 4 drug-related toxicity. Provide justification for any exceptions. To provide guidelines for recurrent Grade 3 events. To require permanent discontinuation for cases meeting Hy's law criteria. Alternatively provide justification for why this is not necessary. 	As additional safety measures
7.1 Discontinuation of Study Intervention	Deleted text referring to Investigator determination of whether or not to discontinue study interventions for liver injury or cardiac changes	As there is insufficient information to support evidence-based decisions by the Investigators.
9.4.2.1 Part 1A: Dose Escalation	Added that the total daily dose increased must not exceed 100% of the highest total daily dose level considered safe.	For clarity
Appendix 6 Clinical Laboratory Tests; Table 19	In the Table row of "Other Screening Tests", clarified that except for safety laboratory assessments , all study-required laboratory assessments will be performed by a central laboratory.	For clarity
Throughout	Minor administrative, editorial, and document formatting revisions	Minor; therefore, have not been summarized

